### **Subject Exclusion Criteria**

Prisoners

Age<18

Pregnancy

Patients with allergy to Dakin's (sodium hypochlorite) solution

Enrolled in a concurrent ongoing interventional, randomized clinical trial.

This prospectively collected cohort of patients will be compared to the similar historical cohort from 2008-2013. We will review medical charts of the patients admitted to UAMC following the same inclusion and exclusion criteria described above to perform a retrospective review. We will collect the same data points as in prospective cohort.

### **Resources available to conduct the Human Research:**

The study will be conducted at UAMC with the support from the Division of Trauma, Critical Care, and Emergency Surgery. We have a dedicated research team to support this project which includes a research coordinator, four research fellows, 24/7 coverage by research nurses and 2 research assistants trained to conduct human research studies, as well as support from the trauma surgeons to identify eligible patients. Patients will be consented by the PI, other trauma attending surgeons, research coordinator or the research fellows, who all have been fully trained in human research.

### **Recruitment Methods and Consenting Process:**

The attending trauma surgeon will identify eligible patients for the prospective cohort. Recruitment and consent will happen in person with a thorough explanation of the treatment protocol by the PI, trauma surgeons, research coordinator or a research fellow. Patients or their Legal Authorized Representatives (LAR) will be informed about the study and consented. Should the patient or the LAR decline participation in the study, immediate cessation of data collection will take place and their information will not be included in the final data analysis.

Retrospective cohort of patients will be identified through medical chart review and we request waiver of consent for this patient population under 45 CFR 46.116(d) and 21 CFR 50.55 (d) as this retrospective research involves no more than minimal risk to subjects, doesn't alter the treatment or management in anyway as it had

already been completed, and it could not practicably be carried out without the waiver as those patients have completed their treatment and it would be extremely hard to obtain consent.

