**PI: [name]**

**The University of Arizona**

**[name]**

**[name]**

**T: [contact]**

## Sample Size: 20 subjects

### Introduction:

Postoperative surgical site infection (SSI) remains a common and serious complication after emergency abdominal surgery with incidence varying between 14 to 32% (1, 2). Seamon et al in a study of 503 trauma patients who underwent laparotomies for *any* enteric injuries demonstrated that primary closure leads to a 3 fold increase in SSI rate (32.1% vs. 9.8%) and 3 fold increase in fascial dehiscence (8.6% vs. 2.6%) compared to wounds managed with delayed closure (3). In contrast, an individual undergoing major *elective* operation is expected to have a 2% risk of SSI (4). Among the various gastrointestinal sites, colorectal procedures are associated with the highest risk of SSI due to the change in bacterial flora from largely aerobic gram-positive organisms in the proximal bowel to more virulent anaerobic species in the colon and rectum such as *Escherichia coli*, *Streptococcus*, *Bacteroides fragilis*, *Proteus* and *Klebsiella* (5-8). In a prospective cohort study of 2393 patients undergoing elective colorectal surgeries, Huebner et al. has shown hospital SSI rates varying between 4% to 25.2% and individual surgeon rates varying from 3.7 to 36.1% (9-14). The most feared consequence of SSI is fascial dehiscence and necrotizing soft tissue infections, which can lead to some of the most difficult surgical complications such as large ventral hernias or enterocutaneous fistulas (15-17).

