#### **Study Population:**

This is a prospective cohort study that will be performed at the University of Arizona Medical Center (UAMC), a Level I Trauma center. Patients who undergo emergent surgery for trauma induced enteric injuries

involving the stomach, small bowel, or colon (ex: gun-shot wounds, stab wounds, blunt colon perforation) or the non-traumatic emergent general surgical pathologies involving the above hollow viscera.

Retrospective review of our database over the past 3 years identified total of 276 patients: 157 patients underwent emergent surgery for trauma related colon injuries and 43 patients due to acute perforated diverticulitis. In addition, 76 patients underwent emergent abdominal surgery for perforated viscus excluding colonic pathologies. Based on these results, we conservatively estimate an average of 90 patients per year will require emergent abdominal surgery for perforated viscus. Thus, we anticipate **enrolling 20 patients** over the 1 year period. This will be followed by data collection, follow-up period, data analysis and report/manuscript about research findings.

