### **Procedures Involved in the Human Research:**

We will approach patients upon the diagnosis to consent them for this prospective study. During the process, the details of the trial will be reviewed along with potential risks and benefits, the endpoints of interest and the process by which these endpoints are evaluated. When notified of trial enrollment, the patient or their legal representative will be given the opportunity to withdraw from further data and sample collection. Those who consent will be enrolled to collect data on outcomes, baseline parameters and follow-up period to evaluate efficacy of VeraFlo for management of contaminated abdominal wounds after emergent surgery. VAC with 1/4% Dakin's solution will be placed immediately at the end of the surgery for the first 3 postoperative days, followed by delayed primary closure on postoperative day 4. Wound will be swabbed at the end of surgery before placing the VAC and before skin closure on Day 4. All follow-ups will be performed as a standard of care.

Data collected will include the following: demographics (i.e. BMI), hemodynamic parameters at the time of presentation and operation, source of infection, imaging studies outcomes, lab tests, surgical procedure performed and its duration, vasopressors, estimated blood loss and transfusion records, antibiotics used and duration, comorbidities (Charlson Morbidity Index, APACHE II), trauma registry data, and complications (if any) during their hospital stay and follow-up in clinic, length of stay (in ICU and in hospital), intra-abdominal wound culture, wound closure details, pain level, cost, wound appearance (recorded by photograph), wound culture, infection, time of nursing care.

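### No rule is stated for which of about 90 potential patients a year become the 20 VeraFlo patients, and no screening log is kept, so the historical SSI comparison may be biased in an uncertain direction

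*Combined protocol and SAP*

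**What the plan says.** All references are to the combined protocol and SAP.

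- **Who finds patients.** Recruitment Methods and Consenting Process: "The attending trauma surgeon will identify eligible patients for the prospective cohort". If a patient or representative declines, "immediate cessation of data collection will take place and their information will not be included in the final data analysis".
- **When.** Procedures Involved in the Human Research: "We will approach patients upon the diagnosis to consent them for this prospective study"; those who consent are then enrolled. The Data Collection Flow Sheet also ticks eligibility and informed consent in the operating-room column.
- **How many, from how many.** The front matter gives "Sample Size: 20 subjects". Study Population says "we conservatively estimate an average of 90 patients per year will require emergent abdominal surgery for perforated viscus", and from this anticipates 20 enrolments in a year.
- **Controls.** The text under Subject Exclusion Criteria says "We will review medical charts of the patients admitted to UAMC following the same inclusion and exclusion criteria described above". Statistical Analysis narrows these to patients who had wet-to-dry dressing changes. It then matches them to the treated patients by propensity score on demographic, severity and laboratory variables.
- **Design.** The Design checklist marks the study non-randomised and single-arm. Statistical Analysis confirms that there is no concurrent comparator.

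Nowhere does the readable text say that eligible patients are approached consecutively, that a screening log is kept, or that eligible but non-enrolled patients are counted.

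**The concern.** With no concurrent arm, the SSI comparison depends on the 20 treated patients being a known sample of the patients the criteria describe. Here the route from about 90 potential patients to 20 enrolled ones is not laid down or recorded. If surgeons bring some kinds of patient forward more readily than others, the SSI rate in the 20 reflects that choice as well as the device.

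The control side is selected too. The Introduction says that wound management after these operations is largely left to the surgeon's preference, so having had wet-to-dry dressings marks a past surgeon's decision. Matching balances only what is recorded and used. Neither degree of wound contamination nor the surgeon's reason for offering the study is named among the matching variables. Analysts could not repair this later, because a screening log cannot be reliably rebuilt after the event.

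**Working it through.** **1. The pool (Study Population).** "Retrospective review of our database over the past 3 years identified total of 276 patients", made up of 157 + 43 + 76 = 276. Per year: 276/3 = 92. The plan states 90, described as conservative, so its figure is reproduced.

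**2. The fraction enrolled.** 20/90 = 22.2%, leaving 90 − 20 = 70 (78%). The 90 is counted before exclusions and consent. If only E of the 90 are eligible, the fraction is 20/E: 33% for E = 60 and 44% for E = 45. So 22% is a lower bound, provided that the 90 includes everyone who meets the criteria. The 90 counts perforated viscus, whereas the inclusion criteria do not require perforation, so this proviso is an assumption.

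**3. Where selection can enter.**

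| Step | Treated series | Historical controls |
|---|---|---|
| Entry | Identified by the attending surgeon; consent required | Chart review under the same criteria |
| Further filter | Decliners dropped; no log | Must have had wet-to-dry dressings |
| Adjustment | Matching on recorded variables | Same |

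Both columns contain a surgeon's decision, made for reasons that the plan does not record. The two need not act in the same direction.

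**4. Scale, as illustration only.** The documents give no SSI risk by type of patient. Assume no treatment effect, half the pool at a lower risk L and half at a higher risk H. If a share s of the 20 is lower-risk, the expected rate is s × L + (1 − s) × H. The first pair uses the ends of the 14% to 32% range in the Introduction, treated as patient risks by assumption. The second is a wider assumed spread.

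| s | L = 14%, H = 32% | Chance of ≤1 SSI in 20 | L = 5%, H = 32% | Chance of ≤1 SSI in 20 |
|---|---|---|---|---|
| 50% (no selection) | 23.0% | 3.7% | 18.5% | 9.3% |
| 75% | 18.5% | 9.3% | 11.75% | 30.1% |
| 90% | 15.8% | 15.2% | 7.7% | 53.7% |
| 100% | 14.0% | 20.8% | 5.0% | 73.6% |

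Selection towards higher risk moves the rate the other way by the same amount: with s = 25%, 0.25 × 14 + 0.75 × 32 = 27.5%, or 4.5 points above 23%. All these figures are before matching, which would remove the part explained by recorded variables, and they ignore selection among controls.

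**5. Time needed under a consecutive rule.** With eligible fraction e and consent rate c, months = 12 × 20/(90 × e × c).

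- e = 1, c = 100%: 2.7 months
- e = 1, c = 50%: 5.3 months
- e = 1, c = 25%: 10.7 months
- e = 0.5, c = 50%: also 10.7 months
- e × c = 20/90 = 22%: 12 months

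Subjects are followed to a two-week clinic visit, so at 10.7 months the last visit falls at about 11.2 months, within the year but with little to spare.

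**The case against.** The strongest reply is that the plan already implies the rule. Identifying eligible patients is case-finding rather than choosing. Patients are approached at diagnosis, those who consent are enrolled, and research nurses are on cover around the clock. A fully consecutive approach with modest eligibility and consent could itself yield 20 a year from 90. **This stands in part:** the ratio 20/90 is not evidence of discretion, and a reader who infers that surgeons are to hand-pick 22% of eligible patients goes beyond the text. But an implied rule does not bind anyone, and without a log nobody could show that it was followed.

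Second, consent at diagnosis usually comes before the wound is seen, so selection on its appearance is unlikely. **This stands in part:** the flow sheet also allows eligibility and consent in the operating room, and a surgeon's preoperative impression can influence selection too.

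Third, the Enrolling Process heading just before the References has nothing under it. A flow chart may have been lost there in text extraction, and it could contain the rule. **This stands** and limits how firmly the gap can be asserted.

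Fourth, the illustrated shifts are modest beside chance. At 23% the standard error of the treated rate is √(0.23 × 0.77/20) = 9.4 points, against shifts of 4.5 to 9 points for the 14%/32% pair. **This stands** as a comment on detectability. Bias of that size would still move the estimate, and matching on recorded variables would not remove the unrecorded part.

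**Conclusion.** The point holds as a gap in the enrolment rule with a real but unquantified risk of bias. On the plan's own count, at least 22% of eligible patients would be enrolled and the rest go undescribed, assuming that the 90 contains all who are eligible and that 20 are reached. Matching on the listed groups of variables cannot correct unmeasured selection by the surgeon. The conclusion depends on the possible missing flow chart not supplying the rule.

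Four stronger readings are not supported:

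- **Controls come from all eligible charts.** Statistical Analysis restricts them to wet-to-dry recipients and matches them.
- **The bias must favour VeraFlo.** Both series are selected, so the net direction is uncertain.
- **The 32.1% and 9.8% in the Introduction give high- and low-risk strata.** They are SSI rates by closure method (primary against delayed), not by patient risk, and are not used here.
- **Consecutive enrolment would make a lower SSI rate attributable to VeraFlo.** Consent selection, calendar time and the non-randomised comparison would remain.

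Because the change affects who is enrolled, it is more than a missing detail and should be made.

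**What to change.** First check whether a figure belongs under the Enrolling Process heading and whether it states an approach rule. If it does not:

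1. In Recruitment Methods and Consenting Process, require that every consecutive eligible patient be approached and every consenting one enrolled until 20 are reached.
2. Have the existing research staff keep a de-identified log of numbers screened, eligible, approached, consented and enrolled, with reasons for non-enrolment. Kept this way, it need not hold clinical data on decliners.
3. Report these counts with the results.

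**Cost:** a sentence or two of protocol text and a little logging work for staff already on cover. Enrolment may be concentrated earlier in the year. If eligibility times consent falls below about 22%, 20 patients would not be reached in a year, but enrolling only some of the consenting patients would be slower still.

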### **Procedures Involved in the Human Research:**

We will approach patients upon the diagnosis to consent them for this prospective study. During the process, the details of the trial will be reviewed along with potential risks and benefits, the endpoints of interest and the process by which these endpoints are evaluated. When notified of trial enrollment, the patient or their legal representative will be given the opportunity to withdraw from further data and sample collection. Those who consent will be enrolled to collect data on outcomes, baseline parameters and follow-up period to evaluate efficacy of VeraFlo for management of contaminated abdominal wounds after emergent surgery. VAC with 1/4% Dakin's solution will be placed immediately at the end of the surgery for the first 3 postoperative days, followed by delayed primary closure on postoperative day 4. Wound will be swabbed at the end of surgery before placing the VAC and before skin closure on Day 4. All follow-ups will be performed as a standard of care.

Data collected will include the following: demographics (i.e. BMI), hemodynamic parameters at the time of presentation and operation, source of infection, imaging studies outcomes, lab tests, surgical procedure performed and its duration, vasopressors, estimated blood loss and transfusion records, antibiotics used and duration, comorbidities (Charlson Morbidity Index, APACHE II), trauma registry data, and complications (if any) during their hospital stay and follow-up in clinic, length of stay (in ICU and in hospital), intra-abdominal wound culture, wound closure details, pain level, cost, wound appearance (recorded by photograph), wound culture, infection, time of nursing care.

### **Specific Study and/or Reference Product(s) Treatment Protocol(s):**

#### **Risks to Subjects:**

This protocol involves minimal risk. Currently, use of VAC therapy to manage contaminated abdominal wounds is an accepted practice. Dakin's solution has been commonly used in clinical practice in wet-to-dry dressing changes. This protocol, which involves the delivery of 1/4% Dakin's solution through the VAC VeraFlo to contaminated abdominal wounds, will formally establish the safety and efficacy of this technique. In addition, this protocol involves microbiological wound culture which is routinely done to patients with contaminated wounds. The risk of the proposed protocol is the same as clinical care.

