#### **Statistical Analysis:**

#### **Sample Size Calculation:**

- A. Event Rate Assumption(s): <5%
- B. Study Group (%): 100%
- C.  Comparator or  Sham Group (%): historic cohort from previous 3 years.
- D. Power Estimation:  95%  90%  85%  80% or Other – Specify: \_\_\_\_%
- E. Evaluable Rate Consideration: Specify: \_\_\_\_%
- F. Sample Size Calculation: 20 Total Number of Subjects. When population is not divided evenly, please specify how it will be divided and rationale for doing so:
- G. Interim Analysis - Sample Size Re-calculation:  Yes  No  Specify rationale:
- H. Number of Centers Projected: 1

This is an observational prospective study with no concurrent arm for comparison; we will use historic data from our center over the last 3 years to analyze results. The advantage of this approach is that there was no change in medical providers among trauma surgeons in the last 3 years. We also have a robust prospectively collected trauma registry that allows performing this analysis. We will identify patients who have undergone emergent abdominal surgery with hollow viscus violations, and had undergone wet-to-dry dressing changes. A Propensity matching analysis will be performed to match patients from the historic cohort to the current patients by demographics, disease severity and laboratory tests. A univariate analysis, independent t-test, and a Kaplan-Meier survival analysis will be performed to compare rate of infection, time-to-closure, and cost analysis.

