#### **Potential Benefits to Subjects and/or Society:**

Current literature shows strong independent benefits of using Dakin's solution and the negative pressure VAC therapy for managing open contaminated wounds. The solution and the device have also been shown not to be harmful. Currently, there is no standard management protocol regarding the combined utilization of Dakin's solution with VAC therapy, a capability delivered by the KCI VeraFlo. This study aims to study the utility and safety of using the VeraFlo with 1/4% Dakin's solution in managing contaminated abdominal wounds. If it is associated with less SSI and earlier achievement of wound closure, then this technique may serve to standardize the management of contaminated abdominal wounds. It has the potential to decrease the time and resource spent on managing open abdominal wounds as compared to the most common technique of wet-to-dry dressing changes. In addition, this technique has the potential to drastically improve patient comfort, convenience and satisfaction.

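### The protocol says the study will formally establish safety and efficacy, but 20 non-randomized patients can only give preliminary estimates: even 0/20 infections cannot confirm <5% or exclude the cited 9.8%

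*Combined protocol and SAP*

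**What the plan says.** Under Risks to Subjects, the protocol says that delivering the solution through the device "will formally establish the safety and efficacy of this technique". The sentence carries no qualification.

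The rest of the plan describes a small study:

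- The Design section marks it non-randomized, single-arm and reference-controlled.
- The sample size section gives "Sample Size Calculation: 20 Total Number of Subjects", the entry "Event Rate Assumption(s): <5" (per cent), and as comparator a "historic cohort from previous 3 years". It does not name the event behind the <5%. I take it to be SSI because that is the primary outcome.
- That section gives no comparator rate, significance level, sidedness, margin or success criterion. No power level appears as selected, but tick marks may have been lost in the text I have, so I do not rely on that.
- The only SSI rates given for emergency or trauma surgery are in the Introduction. One is an "incidence varying between 14 to 32" per cent; the other is a trauma laparotomy study with an "increase in SSI rate (32.1% vs. 9.8" per cent, for primary against delayed closure.

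Other sections are more modest. Clinical Hypotheses speaks of a low infection risk, and Potential Benefits says the study aims to examine utility and safety.

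**The concern.** To establish efficacy or safety formally, a study needs a criterion fixed in advance and enough information to meet it. This plan has no criterion, and 20 patients give wide limits around any observed proportion.

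The risk is in how a good result would be read. Zero or one infection is likely if the true rate is near 5%. Under the protocol's own sentence, such a result would count as established safety and efficacy. Yet it would be compatible with the rate the Introduction cites for delayed closure, and delayed primary closure is itself part of the study technique. The same applies to adverse reactions to the solution, a named safety endpoint: seeing none in 20 patients does not show that they are rare.

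**Working it through.** **The plan's own figure.** The number 20 cannot be reproduced or refuted, because the inputs are incomplete. One set of assumed inputs does return it: an exact single-arm test of a true 5% against a fixed 32%, one-sided 0.025, power at least 90%, needs 20 patients and succeeds with 2 or fewer infections. The plan states neither that test nor that null rate, so this is not a reproduction. Study Population points to another origin: 276 cases in 3 years (276/3 = 92, taken as about 90 a year), from which 20 enrolments are expected in one year.

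**Inputs.** n = 20 and <5% (Sample Size Calculation); 9.8%, 14%, 32% and 32.1% (Introduction). Sidedness is not stated, so both versions are shown.

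**Step 1: the best possible result.** For 0 events in n, the exact (Clopper-Pearson) upper limit is 1 − a^(1/n), with a = 0.025 two-sided or 0.05 one-sided.

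- Two-sided: 1 − 0.025^(1/20) = 16.8%
- One-sided: 1 − 0.05^(1/20) = 13.9%

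**Step 2: other favourable results (exact limits).**

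| Infections | Two-sided 95% interval | One-sided 95% upper limit |
|---|---|---|
| 0/20 | 0 to 16.8% | 13.9% |
| 1/20 | 0.1% to 24.9% | 21.6% |
| 2/20 | 1.2% to 31.7% | 28.3% |

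**Step 3: which rates 0/20 excludes.** The probability of 0/20 at a true rate p is (1 − p)^20. A rate is excluded two-sided if this is below 0.025, and one-sided if it is below 0.05. With zero events, the smallest n that excludes p is ln(a)/ln(1 − p), rounded up.

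| True rate p | P(0/20) | Excluded by 0/20? | n with zero events, two-sided / one-sided |
|---|---|---|---|
| 5% | 0.358 | no | 72 / 59 |
| 9.8% | 0.127 | no | 36 / 30 |
| 14% | 0.049 | one-sided only, just | 25 / 20 |
| 32% | 0.0004 | yes | 10 / 8 |

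Zero is the most favourable count, so no result in 20 patients can confirm <5% or exclude 9.8%. If the true rate is 5%, at least one infection occurs with probability 1 − 0.358 = 64%.

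**Step 4: the comparison with historic controls.** The matching ratio is not stated. I assume 1:1 or 1:3 and treat the groups as independent. Fisher exact power to show a lower rate, at two-sided 0.05 with a true 5% on study treatment:

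| Control rate | 20 v 20 | 20 v 60 |
|---|---|---|
| 9.8% | 1.5% | 0.5% |
| 14% | 5.5% | 4.6% |
| 32% | 50% | 74% |

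The outcome of the comparison therefore depends mainly on a control rate that the plan does not give.

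**Step 5: safety.** For adverse reactions to the solution, 0/20 gives the limits of Step 1: a true rate up to 13.9% (one-sided) or 16.8% (two-sided) remains possible.

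**The case against.** The strongest case for the plan is that the study can learn something real. If the right benchmark is about 32%, then 0, 1 or 2 infections in 20 would each exclude it two-sided, and the single-arm test described in the working has 92.5% power at a true 5%. The planned comparator is the centre's own wet-to-dry cohort. If its rate lies near the top of the cited range, 20 patients could show a difference. The 9.8% comes from a single trauma study and is not that cohort's rate.

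This stands, and it rules out several stronger readings:

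- *That 0/20 excludes none of the cited rates.* It excludes 32% and 32.1% clearly. On 14% the answer depends on sidedness, which the documents do not state.
- *That <5% is a success threshold the study must meet.* It is entered as an assumption, in a different section from the claim, without a named event.
- *That the protocol announces a change of practice.* The sentence in Potential Benefits, "then this technique may serve to standardize the management of contaminated abdominal wounds", is conditional on less SSI and earlier closure, and says only that the technique may serve this purpose.
- *That 276 controls are available.* That count covers all emergent cases found in the review. The plan restricts controls to wet-to-dry patients and then matches them.

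It can also be said that the claim is one sentence outside the hypotheses and the analysis, and that Study Population already ties 20 to accrual. Both are true and limit the weight of the point. Neither makes the sentence correct. Excluding about 32%, a figure that matches the cited primary-closure rate, would not settle the planned comparison with wet-to-dry dressings, and it would leave safety where Step 5 puts it.

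**Conclusion.** The point holds, limited to the stated conclusion. The design cannot formally establish safety and efficacy. Even a perfect result leaves an upper limit of 16.8% (two-sided) or 13.9% (one-sided). It cannot confirm <5% or exclude 9.8% on either basis, and two-sided it cannot exclude 14%. It would exclude about 32%, so a reader should not infer that the study is uninformative, or that it needs more patients for the purpose its design can serve.

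This rests on the following:

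- The <5% refers to SSI.
- The cited rates stand in for the site's wet-to-dry rate, which is not given.
- All 20 patients are evaluable; the evaluable-rate entry holds no figure, and fewer would widen the limits.
- Infections are fully ascertained. Follow-up to a two-week visit is shorter than the 30- and 90-day windows in the SSI definitions, so an observed 0/20 could be an undercount. Those sections need to be reconciled.

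**What to change.** - **Risks to Subjects:** replace the claim with a statement that the study will provide preliminary estimates of the SSI rate and of adverse reactions.
- **Sample Size Calculation:** state that 20 is set by feasibility, as Study Population implies.
- **Statistical Analysis:** report the SSI proportion and the proportion with an adverse reaction to the solution, each with an exact 95% confidence interval, alongside the matched historical comparison. Say whether the intervals are one- or two-sided, since the answer at 14% depends on it.

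The cost is a change of wording and two intervals added to the analysis, with no extra patients, procedures or data. The downside is that the stated claim becomes less favourable.
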